# 8.4 Analysis of the Secondary and Tertiary Outcomes.

Analysis of opioid medication dose will also be implemented as a linear mixed effects model of longitudinal morphine equivalent intake, conditional on baseline, under a log transformation to reduce skew. Distress and other psychological outcomes will similarly be analyzed using linear mixed models adjusted for randomization imbalance by covarying baseline levels of the outcome. Exact unadjusted p-values are reported for the secondary and tertiary outcomes. As in the analysis of our continuous primary outcomes, our primary interest lies in the adjusted main effect of treatment, which with this model specification represents the average effect of treatment across all post-treatment measurement points.

Control for multiple comparisons among the secondary and tertiary variables is provided by a global hypothesis test evaluated at alpha=.05 in the multivariate mixed effects model as  $H_{0,\mathrm{joint}}: \forall j, \delta_j = 0$  versus  $H_{1,\mathrm{joint}}: some \ \delta_j \neq 0$  for some j. Multivariate contrasts may be

implemented in the univariate mixed model framework of SAS 9.4 by introducing a categorical indicator variable for outcome j, interacting this variable with all other effects, and specifying distinct covariance matrices for each j. The global net benefit hypothesis is a custom contrast with J df, where J is the number of non-primary outcomes. Rejection of the global hypothesis test implies a significant treatment impact on at least one secondary outcome j, and we report exact p-values for the univariate tests.

Descriptive analysis of opioid dosing data will examine group differences in the proportion of participants who achieve an opioid dose reduction of ≥50% at each time point.

To explore whether the cognitive, affective, and physiological mediators specified in Aims 2 and 3 statistically mediate the effect of treatment on outcome variables, we will conduct structural equation path analyses according to established guidelines by evaluating three regression paths: A) 'a' path between treatment indicator and change in outcome (e.g., opioid misuse) from pre-treatment to follow-up; B) the 'b' path between pre-post treatment change in the mediator (e.g., attentional bias) and pre-treatment to follow-up change in the outcome (e.g., opioid misuse); and C) the 'c' path between treatment and pre-post treatment change in the mediator (e.g., attentional bias). We will test mediation by evaluating the significance of the joint product of the a and b paths, with bootstrapping used to test the significance of the indirect effect. Our team developed a comprehensive analysis of mediation under possible moderation for clinical trials, allowing for the possibility that treatment has changed relationships, not just levels, among variables - this will further guide analyses for Aims 2 and 3. Path models will be corrected for multiple comparisons. Mediational analyses will be published in a subsequent report following publication of the primary trial outcomes.

For EMA, we will use growth curve analysis to examine treatment and homework practice effects on: trajectories of craving (and other tertiary EMA outcomes – e.g., affective state). The basic growth curve model will be specified with fixed effects consisting of continuous time t (in days), categorical period p (AM, Noon, or PM reporting) and the categorical between-subjects treatment factor (g = MORE vs. SG). Random effects will incorporate correlated intercept and period-specific trend components, as in standard growth models:

$$y_{itpg} = b_{0i} + b_{1ipg}t + \varepsilon_{itpg} ; b_{0i}, b_{1ipg} \sim MVN([\beta_{0p}, \beta_{1pg}]', \Psi), \varepsilon_{itpg} \sim N(0, \sigma^2).$$

The model allows different trends in the three different reporting periods of the day. The key null hypothesis of treatment impact in EMA will be evaluated by testing the equality of the three fixed effect period trends between arms:

$$H_0: \sum_{p} \beta_{1p,g=SG} / 3 = \sum_{p} \beta_{1p,g=MORE} / 3 = \sum_{p} \beta_{1p} / 3$$

Additional temporal complexity and serial dependence will be considered in polynomial and autoregressive models, as evaluated with the Bayesian Information Criterion. More complicated relationships will be considered in ALT models that include additional cross-lagged and autoregressive effects.

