## 2. AIMS

AIM 1. To conduct a RCT of the Mindfulness-Oriented Recovery Enhancement (MORE) intervention for co-occurring aberrant drug-related behaviors and chronic pain in primary care.

We will compare the therapeutic impact of MORE and a conventional supportive group (SG) psychotherapy active control condition on clinical outcomes germane to opioid misuse and chronic pain. Hypotheses: Opioid misusing patients assigned to MORE, as compared to SG participants, will evidence decreased opioid misuse and pain (*PRIMARY OUTCOMES*), as well as reduced opioid craving, opioid dosing, and psychological distress (*SECONDARY OUTCOMES*) from pre- to post-treatment through 9-month follow-up.

AIM 2. To test and quantify the degree to which MORE's impact on opioid misuse and pain is mediated by proactive control over emotion-cognition interactions (top-down mechanism).

Hypotheses: The impact of MORE on opioid misuse and pain will be mediated by improvements in: **a)** attentional disengagement from opioid-related cues (reduced attentional bias); **b)** emotion regulation; and **c)** cognitive coping (e.g., reinterpretation of pain as innocuous sensory information).

AIM 3. To test and quantify the degree to which MORE's impact on aberrant drug-related behaviors is mediated by restructuring of reward processing (bottom-up mechanism).

Hypotheses: The impact of MORE on aberrant drug-related behaviors will be mediated by restructured reward processing, as indicated by **a)** decreases in psychophysiological indices of opioid cue-reactivity; **b)** increases in responsiveness to natural reward cues; and **c)** a shift in the relative salience of these cues.

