## 3. STUDY DESIGN

A two-arm parallel RCT design with an active control group will minimize internal threats to validity. Mindfulness-Oriented Recovery Enhancement (MORE; n=130) and the Supportive Group Psychotherapy control (SG; n=130) will be equated for time spent in treatment. Assessors will be blind to treatment condition. Target sample sizes were determined via power and precision analyses. The unit of randomization is the individual patient. The co-primary outcomes are opioid misuse and chronic pain symptoms. Participants will complete a clinical assessment battery at pre- and post-treatment, and at 3-, 6-, and 9-month follow-ups. Participants will complete a psychophysiological assessment protocol at pre- and post-treatment. Participants will complete ecological momentary assessments (EMAs) of symptoms, skill practice, and opioid use during treatment and 1 month afterward up to 3 times/day (morning, noon, and night).

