## 4.3 Tertiary Outcomes

The tertiary outcomes include psychophysiological measures, self-report mediators, and other EMA ratings of momentary affective state and momentary pain ratings.

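### The single global test in Section 8.4 controls multiplicity only weakly, and its rejection does not show an effect on a secondary outcome

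*SAP*

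**What the plan says.** Section 8.4 gives one device against multiplicity outside the primary outcomes: "Control for multiple comparisons among the secondary and tertiary variables is provided by a global hypothesis test evaluated at alpha=.05". The null hypothesis is that every treatment contrast is zero, and the alternative is that some contrast is not. The degrees of freedom and the reading of a rejection are given as: "J is the number of non-primary outcomes. Rejection of the global hypothesis test implies a significant treatment impact on at least one secondary outcome".

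For individual outcomes the section says: "Exact unadjusted p-values are reported for the secondary and tertiary outcomes". No per-outcome threshold or step-down rule follows, and the section does not say whether the univariate tests are read only after the global test rejects.

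The contrast for each outcome "represents the average effect of treatment across all post-treatment measurement points", conditional on baseline.

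The SAP keeps the two tiers apart. Its synopsis and Section 4.2 name three secondary outcomes: opioid dose, psychological distress and opioid craving. Section 4.3 says: "The tertiary outcomes include psychophysiological measures, self-report mediators, and other EMA ratings". Craving is measured by EMA, which runs "during treatment and 1 month afterward up to 3 times/day" (Section 3), and Section 8.4 gives it a separate model: "For EMA, we will use growth curve analysis".

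**The concern.** Three things look wrong, and a fourth needs tidying.

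- **Weak control.** An omnibus test at .05 limits error only when all its outcomes are null. After a rejection driven by one real effect, it says nothing about which other outcomes respond.
- **Wrong inference.** The test covers all non-primary outcomes, so its rejection cannot be attributed to the secondary tier. The trial itself expects movement in the tertiary tier: Aim 2 states "The impact of MORE on opioid misuse and pain will be mediated by improvements in" and then lists mediators, and Section 4.3 counts the self-report mediators as tertiary.
- **Craving.** The tested contrast is a baseline-adjusted average over post-treatment assessments. Craving has no pre-treatment entry in Table 1 and is tested as a difference in slopes. Whether and how it enters the global test is not stated.
- **Section 4.** One sentence there applies Bonferroni to all outcomes, while Section 8.3 applies it to the three primary variables and Section 8.4 does not use it. It may be meant for the primary variables only.

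At stake is the reporting of dose, distress and craving. If only mediators respond, the SAP's own sentence would report a secondary effect that does not exist.

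**Working it through.** **Inputs from the SAP.** Global test at .05 with J degrees of freedom; J is the number of non-primary outcomes; three secondary outcomes; two-sided tests (Section 4). Table 1 names 4 self-report mediators and 6 other tertiary measures, so 10 tertiary scales.

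**Assumptions, because the SAP gives no values.** J = 12 (dose, distress and the 10 scales) or J = 13 (craving added). The J test statistics are normal with equal correlation r of 0, .3 or .5. One or two tertiary outcomes truly respond, each with expected test statistic z. Univariate p-values are read at .05 after the global test rejects. Simulations used 400,000 draws.

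**Step 1: the stated 5%.** With every outcome null and J = 12, the test rejects in .050, .050 and .051 of draws for r = 0, .3 and .5. The stated alpha is reproduced.

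**Step 2: rejection when no secondary outcome responds (J = 13).** With one real tertiary effect, the statistic is noncentral chi-square with 13 df and noncentrality

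λ = z² × [1 + (J − 2)r] / {(1 − r)[1 + (J − 1)r]}.

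For z = 4:

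- r = 0: λ = 16 × 1 = 16
- r = .3: λ = 16 × 4.3 / (.7 × 4.6) = 21.4
- r = .5: λ = 16 × 6.5 / (.5 × 7) = 29.7

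The probability of exceeding the .95 quantile of chi-square with 13 df (22.36) is:

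| Real tertiary effects | r = 0 | r = .3 | r = .5 |
|---|---|---|---|
| one, z = 4 (formula) | .743 | .881 | .972 |
| two, z = 4 (simulated) | .982 | .996 | 1.000 |
| one, z = 2.5 (simulated) | .299 | .404 | .566 |

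In all of these the three secondary outcomes are null, so every rejection would be misreported under the SAP's sentence. With one effect at z = 4, the test rejects in 62% to 85% of draws without any secondary p-value below .05.

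**Step 3: false positives on the secondary outcomes.** Share of draws in which the global test rejects and at least one null secondary outcome has |z| above 1.96 (z = 4):

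| Setting | r = 0 | r = .3 | r = .5 |
|---|---|---|---|
| J = 13, three secondary, one real effect | .126 | .130 | .125 |
| J = 13, three secondary, two real effects | .142 | .136 | .125 |
| J = 12, dose and distress, one real effect | .087 | .092 | .090 |
| J = 12, dose and distress, two real effects | .097 | .095 | .091 |

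The ceiling with independent outcomes is the rate with no gate: 1 − .95³ = .143 for three outcomes and 1 − .95² = .0975 for two. For J = 13 the range over z = 2.5 to 5 is 7% to 14%. For J = 12 with one real effect at z = 2.5 it is 5% to 7%. Counting every null non-primary outcome, the z = 4 range is 29% to 43%, mostly from tertiary outcomes.

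**Step 4: smaller family.** If the global test covered only the three secondary outcomes and one truly responded, at least one of the other two would be falsely positive in about 9% to 10% of draws (expected z of 3 to 8). The weakness does not depend on a large J.

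**Step 5: Holm.** Holm over the three secondary outcomes, in the J = 13 runs, gives .044 to .050.

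**The case against.** The SAP labels the univariate p-values as unadjusted and nowhere says that each may be declared significant. The rule of reading them at .05 after rejection is supplied here, and with it the false-positive rates come close to those of two or three plain unadjusted tests. That is fair as to size. But the SAP does not merely report p-values: it says that control for multiple comparisons is provided, and labelling does not make that claim true for individual outcomes.

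The sentence on rejection may be loose wording, since the same section states the correct alternative and defines J over all non-primary outcomes. Changing one word would cure it. Even so, the SAP separates secondary from tertiary outcomes throughout, so the sentence is wrong as written.

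The scenario is chosen: Aim 1 expects the secondary outcomes to improve too, and J of 12 or 13 leaves out the psychophysiological measures and the EMA affect and pain ratings. With J = 20 or 30 and one effect at z = 4, rejection falls to .65 to .95 or .55 to .91. The size changes and the direction does not. Section 8.4 also promises multiplicity correction for the mediation path models, but that does not remove the mediators from J.

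Craving does have its own model and null hypothesis; only its place in the global test is missing. The Section 4 sentence is ambiguous and not a proven contradiction.

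Finally, recruitment has ended (Section 6.2) and parts of Section 8.3 are in the past tense, so a change of procedure may come late. This calls for a dated record of the change. Holm only tightens what counts as significant, so lateness is not a reason to leave the text as it is.

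**Conclusion.** The concern holds. The global test controls error only under the complete null, and the stated consequence of rejection does not follow from the hypotheses tested. Both follow from the text alone.

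The size depends on assumed values for J, correlation, effect size and reading threshold. Under those used here, with J = 13 and all secondary outcomes null, the test rejects in 74% to 97% of trials with one tertiary effect at z = 4, and in 30% to 57% at z = 2.5. At z = 4, with one or two real tertiary effects, false positives on the secondary outcomes run at 9% to 10% for dose and distress (J = 12) and 12% to 14% for all three (J = 13).

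This should be corrected, but it does not threaten the trial's main conclusion: the primary tests at .0167 each and the success definition in Section 4 do not use the global test.

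**What to change.** Replace the global gate with Holm at two-sided .05 over dose, distress and EMA craving, each tested in its own planned model. Report tertiary outcomes as exploratory, without significance claims. Another strong-control rule over the three secondary outcomes would also do.

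If the global test is kept, say that rejection implies an effect on at least one non-primary outcome, list the outcomes counted in J, and state whether and how craving enters. This corrects the inference and the craving gap, but leaves individual outcomes without familywise protection, so the claim of control should be limited accordingly.

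In Section 4, limit the Bonferroni sentence to the three primary variables and refer to Section 8.4 for the rest.

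The cost is SAP wording, a dated note of the change, and somewhat stricter secondary thresholds: the smallest of the three p-values is compared with .05/3 = .0167. The primary analysis and the success definition stay as they are.

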Primary Outcome	The primary outcome is opioid misuse measured by the Drug Misuse Index, operationalized as scores on the COMM and triangulated by blinded clinical interview and urine drug screen. The co-primary outcome is chronic pain symptomology, operationalized as pain severity and functional interference scores on the Brief Pain Inventory (BPI).

Primary Analysis	Effects of treatment on the DMI will be analyzed with generalized mixed effects models, and effects on the BPI will be analyzed with mixed effect ANCOVA models, adjusting for baseline levels.
Secondary Outcomes	Opioid dose, psychological distress, and opioid craving.
Interim Analysis	Interim monitoring will focus on patient accrual, baseline comparability of treatment groups, protocol adherence, data completeness and quality, and safety. No interim outcome analysis is planned.

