- a) Replication of the analysis model (1) under simultaneous inclusion of the three primary outcomes of drug misuse, pain severity, and pain interference, repeated over post-randomization assessments, along with respective baseline predictor values. In this multivariate analysis, pain severity and pain interference are continuous variables, while drug misuse is represented as a dichotomous outcome under a logit link. All three outcomes are free to correlate in the analysis, with the global hypothesis test imposed by nonlinear equality constraints on the net benefits  $H_{0j}$ :  $\delta_j = 0$  for j=1,2,3, a 3 df test.
- b) Replication of the 3 df global hypothesis test in (a) with the addition of the continuous log-transformed opioid use secondary outcome, and the continuous Distress secondary outcome as correlated variables.
- c) Replication of (b) with the addition of the demographic predictor variables gender and continuous age at baseline.
- (d-f) Re-running variations a, b, and c under constrained longitudinal analysis (CLDA) rather than regression adjustment for baseline. Under CLDA, the baseline means are constrained to be equal across arms. These constraints are straightforward under multivariate modeling. The overall benefit contrasts among the post-baseline means, conditional on within-outcome baseline treatment arm equalities, are equivalent to the difference in areas under the curve for the conditional post-baseline mean trajectories.

In the text and tables, we report p-values obtained under Model C as  $p_{MAR^+}$ , to indicate that the standard MAR analysis has been supplemented with several auxiliary variables, as described above.

Finally, we re-estimated all analyses under a simple selection model  $^{37,38}$  in which missingness is dependent on the value of the unobserved outcome in as well as the prior observed responses. In the text and table, we report p-values obtained under this model as  $p_{NMAR}$ . The Not Missing at Random designation indicates that this model does not require the more restrictive assumptions of MAR, but may be valid when missingness depends on underlying and unobserved values.

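### The SAS recipe for the global secondary/tertiary test names a covariance matrix per outcome but none between outcomes; coded literally, the nominal .05 test is liberal

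*SAP*

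**What the plan says.** Section 8.4 reports secondary and tertiary p-values unadjusted and assigns multiplicity control for these outcomes to a single "global hypothesis test evaluated at alpha=.05 in the multivariate mixed effects model". The test is "a custom contrast with J df, where J is the number of non-primary outcomes". No value of J is given and the outcomes in it are not listed.

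For the implementation, 8.4 says that the contrasts can be obtained in SAS by stacking the outcomes, "introducing a categorical indicator variable for outcome j, interacting this variable with all other effects, and specifying distinct covariance matrices for each j". The wording is permissive: this is a possible route, not a mandatory one. The section mentions neither a covariance between outcomes nor a robust variance for this test.

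The continuous secondary outcomes follow the form of model (1) in section 8.3. There the random-intercept variance (ψ_j) and the residual covariance (Θ_j) each carry one outcome index, and no term links two outcomes. In the same section, sensitivity variation (a) for the primary outcomes does address the link: "All three outcomes are free to correlate in the analysis". Variation (b) then brings in dose and distress as correlated variables.

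**The concern.** With every fixed effect interacted with the outcome indicator and a separate covariance matrix for each outcome, the likelihood splits into J separate models. The J-df Wald statistic is then the sum of J squared z-statistics, referred to a chi-square (or F) distribution that is correct only if the J treatment estimates are independent. They come from the same patients at the same visits. Many are neighbouring self-report constructs (distress, affect, anhedonia, PTSD symptoms, catastrophizing), so zero correlation is not a credible default.

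This test is the only multiplicity protection that the plan states for non-primary outcomes. If its size exceeds .05 when treatment affects none of them, a claim that at least one has responded carries more false-positive risk than the plan says.

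**Working it through.** **Inputs**
- Nominal size .05 with J df: section 8.4.
- J: not given. The synopsis names three secondary outcomes, "Opioid dose, psychological distress, and opioid craving". Section 8.4 models craving separately by growth curves on momentary assessments, so 2 or 3 secondary outcomes could enter the stacked model. Adding the 4 self-report mediators and 6 other tertiary scales of Table 1 to dose and distress gives 2 + 4 + 6 = 12. Counting PANAS as two scales gives 13. Momentary and psychophysiological measures are left out.
- r, the correlation between treatment z-statistics of different outcomes: not given. The .34 to .56 in section 6.2 are correlations between repeated measures of one outcome and do not supply it. **Assumption:** one common r, from .1 to .5.
- N = 250 enrolled: section 6.2, below Table 2.

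**Direction.** Let Q be the sum of z_j² and R the null correlation matrix of the z_j. Then E(Q) = J whatever R is, and Var(Q) = 2·trace(R²) = 2[J + J(J−1)r²] for a common r. The reference chi-square has variance 2J.
- J = 3, r = .5: 2[3 + 6 × .25] = 9, against 6.
- J = 12, r = .3: 2[12 + 132 × .09] = 47.8, against 24.
- J = 12, r = .5: 2[12 + 132 × .25] = 90, against 24.

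The mean is right and the spread too large. Since r enters squared, the sign of the correlations does not matter to the variance.

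**Size.** With a common r, R has eigenvalues 1+(J−1)r (once) and 1−r (J−1 times), so under the null Q = [1+(J−1)r]·χ²₁ + (1−r)·χ²_{J−1}. For J = 12 and r = .5 this is 6.5·χ²₁ + 0.5·χ²₁₁. The probability that Q exceeds the 95th percentile of χ²_J, from 2,000,000 draws per cell, is:

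| J | r=0 | r=.1 | r=.2 | r=.3 | r=.5 |
|---|---|---|---|---|---|
| 2 | .0499 | .0504 | .0515 | .0533 | .0594 |
| 3 | .0500 | .0510 | .0536 | .0578 | .0695 |
| 12 | .0502 | .0571 | .0730 | .0917 | .1263 |
| 13 | .0498 | .0580 | .0751 | .0945 | .1300 |

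The r = 0 column reproduces the plan's .05: the test is correct if the outcomes are independent.

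**Finite-sample check.** 4,000 simulated trials per row, N = 250, four post-baseline visits, complete data, baseline-adjusted treatment difference in each patient's mean. The simulation standard error at .05 is √(.05 × .95 / 4000) = .0034.

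| J, r | Block-diagonal | Between-outcome covariance included |
|---|---|---|
| 2, .5 | .059 | .052 |
| 3, .5 | .077 | .054 |
| 12, 0 | .052 | .051 |
| 12, .3 | .089 | .052 |
| 12, .5 | .124 | .056 |

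Including the covariance brings the size back to about .05, within simulation error.

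**The case against.** The strongest reply is that the SAP never says the outcomes are independent. It calls the model multivariate and offers the SAS route only as a possibility. Separate matrices per outcome may mean no more than that scales in different units should not share one variance. Interacting the indicator with all other effects could extend to the patient intercept, and outcome-specific intercepts may be allowed to correlate. The team also frees cross-outcome correlation in the section 8.3 sensitivity models. All of this stands. A reader might infer that the plan deliberately assumes independence; the text does not support that. It names no between-outcome covariance, but it excludes none. What remains is that the only stated recipe, followed as written, omits the term on which the .05 depends. The 8.3 statement concerns a different test, of the primary outcomes, and does not fill the gap.

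A second reply is that the large figures need both a large J and a large r. This also stands. A common r of .5 across opioid dose, mindfulness, PTSD symptoms and meaning in life has no support in the document. Section 8.4 itself speaks of a significant result as bearing on at least one secondary outcome, and with J of 2 or 3 the inflation is modest.

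Third, a reader might take the individual secondary p-values to be wrong as well. They are not: each univariate test uses only its own outcome's covariance.

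**Conclusion.** The concern holds as a gap in the recipe that makes its literal coding liberal. If the model is coded block-diagonally, the true size of the nominal .05 global test is about .05 to .07 for J of 2 or 3 and about .06 to .13 for J of 12, for r between .1 and .5. These sizes are conditional on three things that the SAP does not state: the block-diagonal coding, the value of J, and a common r. An analyst who adds the between-outcome covariance unprompted would have a test of about the right size, but the plan should not leave that to the programmer. The effect is confined to the one omnibus statement about non-primary outcomes; the primary tests at .0167 do not depend on it. The plan should be changed, because this test carries all the multiplicity control claimed for those outcomes.

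**What to change.** Keep the outcome-specific covariance matrices in section 8.4 and add two things.

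1. State how between-outcome covariance enters the J-df Wald test, in one of two ways:
   - an empirical (sandwich) covariance clustered on patient, not on patient-by-outcome, with a small-sample correction; or
   - a parsimonious between-outcome covariance, such as correlated outcome-specific patient intercepts plus same-visit residual covariance.
2. List the outcomes that make up J, and say whether craving, the other momentary measures and the psychophysiological measures are in it.

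The sandwich route is the lighter one. A fully unstructured version of the second route is not a small change: at J = 13 each symmetric matrix has 13 × 14 / 2 = 91 parameters, so intercepts and residuals together need 182 from 250 patients. Hence the word parsimonious.

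The cost is a few sentences in the SAP, a little more analysis work and, often, a less favourable global p-value. For example, with equal z on J outcomes and common r, the correct statistic is Jz²/[1+(J−1)r], where the block-diagonal coding gives Jz².
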